## 8. OUTCOME MEASURES

#### 8.1. Internal Pilot Outcome

The success of the 6-month internal pilot study will be based upon the recruitment rate (overall and at individual sites), completeness of primary outcome data (quality of life questionnaires 30 days after surgery in each arm of the study) and adherence to the intervention (adherence in the intervention arm will be defined as using the App at least twice a week in the time before surgery).

We will recruit 125 participants (14% of the total sample) during the 6-month internal pilot phase. We will open 2 sites in the first month, then 3 sites a month for the next 5 months until a maximum of 17 sites are open in the pilot phase.

#### Stop/Go Criteria

We have set criteria relating to number and rate of participants recruited, the number of sites, recruitment rate, data completeness/retention and adherence with the intervention (see Table 1 below):

• GO: progress to main trial; following pilot phase we would still review trial processes to assess whether any changes could/need to be implemented to improve the trial.

• MODIFY: review the trial processes to identify implementable changes. This may include recruiting additional centres and/or retraining centres in trial pathways and procedures. We would discuss with the trial oversight committees and funder about the need for a second internal pilot phase to verify resolution of issues, then if progress is satisfactory continue to the main trial.

• **STOP**: abandon the trial if the trial oversight committees and funder feel this is the appropriate course of action.

Progression criteria	Stop	Modify	Go
Trial recruitment % complete of pilot target (n=125)	<50%	50-99%	≥100%
Average Recruitment rate/ site/ month	<1	1.1-2.1	≥2.2
Number of sites opened	<8	9-16	17
Total number of participants recruited	<63	64-124	≥125
% of participants completing quality of life questionnaires 30 days after surgery in each arm of the study	<50%	50-79%	80-100%
% of participants adherence* with the F4S intervention	<50%	50-79%	80-100%

Table 1: Internal pilot progression criteria (n=125)

#### 8.2. Main Trial Outcomes

### 8.2.1 Primary Outcomes

- Patient-reported quality of physical function scale recovery (using the EORTC-QLQ-C30) at 30 days after surgery
- Surgical complications (using the Comprehensive Complication Index (CCI)) at 30 days after surgery

# 8.2.2 Secondary Outcomes

\* Adherence defined as per section 7.8 Adherence.

- Days Alive and at Home Within 30 days (DAH30)
- Patient-reported quality of life (using the EORTC-QLQ-C30 & LC 29) at 14 days, 30 days, 3 and 6 months after surgery
- Mental health/well-being (using the Hospital Anxiety and Depression Scale (HADS))
- Symptom score (using a 0-10 point VAS) (intervention only)
- Motivational processes
- Physical status assessed by the incremental shuttle walk test (ISWT), sit to stand test and hand grip test
- Patient-generated subjective global assessment short form (PG-SGA SF)

#### 8.2.3 Health Economic Outcomes

- Health Related quality of life (EORTC-QLQ-C30, LC-29 and EQ-5D-5L)
- Health resource usage

# 8.2.4 Patient Reported Outcomes

Patient reported outcomes will be collected via paper booklets (unless stated) administered either during routine hospital visits or posted direct to the participants, they will consist of:

- Patient-reported quality of life (using the EORTC-QLQ-C30, LC 29)
- Mental health/well-being (using the HADS)
- Symptom score (using a VAS) (intervention only obtained from the F4S App)

#### 8.2.5 Clinical Outcomes

Clinical (objective) outcomes are collected at timepoints designed to match routine appointments. Data for these measures are entered by site staff directly onto the trial database.

The ISWT is a valid incremental field walking test to assess the functional capacity in patients with chronic airways obstruction [44,45]. It is a sensitive test that can be used on a wide range of patients with varying disability severity. Further, this validated field test has proven sensitive to changes in pulmonary rehabilitation programmes [46-48]. The equipment needed to perform the ISWT test is simple: CD or MP3 player and two markers (or small cones) placed 9 metres apart and it can be carried out in a flat hospital corridor with minimal blind turns or obstacles [49]. The ISWT has 12 levels; each level is measured by calculating the distance walked to the nearest 10m completed, and the time to complete that distance by the patient should also be recorded [49].

.....

The hand grip strength test is performed using various equipment such as the Jamar Hand Dynamometer [50]. Previous studies have shown grip strength to predict current and future health [50]. When performing the hand grip test, the patient should be seated comfortably in a chair with back support and fixed arm rests, and three measurements for each hand, alternating sides should be recorded [50].

### 9. TRIAL PROCEDURES

## Baseline (at least 2 weeks prior to surgery)

The following procedures and assessments should be performed:

- Medical history
- Informed consent
- Randomisation
- Nutritional assessment including weight and height (PG-SGA SF)
- Physical tests Muscle strength hand grip, ISWT and sit to stand test
- Participant completed questionnaires to include IPAQ-E, EORTC-QLC-C30 & LC29, EQ-5D-5L, HADS, Technology Access Questions

#### F4S Arm only:

o Instructions will be provided to the participants and/or care giver for use of the App

#### **Day of Surgery**

- Nutritional assessment including weight (PG-SGA SF)
- Physical tests Muscle strength hand grip and sit to stand test
- Participant completed questionnaires to include EORTC-QLC-C30 & LC29, EQ-5D-5L,
   HADS
- Pre-operative questions assessing usual care
- Pre-operative Nutritional input assessment (drinks and dietitian)

# F4S Arm only:

- Motivational processes,
- o Shortened scales of behavioural change

# Day of Hospital discharge post-Surgery

- Physical tests Muscle strength hand grip and sit to stand test
- Assessment of in-hospital complications (Comprehensive Complication Index (CCI))

#### 14 days post-Surgery

 Participant completed questionnaires to include EORTC-QLC-C30 & LC29, EQ-5D-5L, HADS

## 30 days post-Surgery

- Assessment of complications post hospital discharge (Comprehensive Complication Index (CCI))
- Nutritional assessment including weight (PG-SGA SF)
- Physical tests Muscle strength hand grip, ISWT and sit to stand test
- Participant completed questionnaires to include EORTC-QLC-C30 & LC29, EQ-5D-5L,
   HADS
- Post-operative questions assessing usual care
- Post-operative Nutritional input assessment (drinks and dietitian)
- Health resource usage questionnaire

### F4S Arm only:

- Motivational processes,
- Shortened scales of behavioural change

# 3 months post-Surgery

 Participant completed questionnaires to include EORTC-QLC-C30 & LC29, EQ-5D-5L, HADS

### F4S Arm only:

- Motivational processes,
- Shortened scales of behavioural change

## 6 months post-Surgery

- Participant completed questionnaires to include EORTC-QLC-C30 & LC29, EQ-5D-5L,
   HADS
- Health resource usage questionnaire
- Assessment of disease recurrence/progression

**Table 2: Schedule of Assessments** 

Trial Procedures and		Day of Surgery	Day of Discharge	14 days Post op	30 days Post op	3 months Post op	6 months Post op
Assessments	Doseline	(- 1	(+/- 2	(+/- 3	(+/- 7	(+/- 2	(+/- 4
	Baseline	days)	days)	days)	days)	weeks)	weeks)
Medical history	Х						
Informed consent	X						
Randomisation	Х						
Patient and/or Carer	X						
Instructions for use of							
Арр							
Nutritional assessment	Х	Х			Х		
(incl. height and							
weight) - PG-SGA SF							
Nutritional input		Х			Х		
assessment (drinks and							
dietitian)							
Physical tests (incl.	Х	Χ*	Х		Х		
hand grip, ISWT, sit to		(ISWT not collected)	(ISWT not collected)				
stand test)			conected)				
Participant completed	Х	Χ*		Х	Х	X	Х
questionnaires (incl.							
EORTC-QLQ-C30 &							
LC29, HADS, EQ-5D-5L)					.,		
Health Resource Usage					Х		Х
questionnaire							
Questions assessing		Χ*			Х		
Usual Care							
Assessment of clinical			X		Х		
complications (CCI)	.,						
Technology Access	Х						
Questions Assessment of disease							V
							Х
recurrence/progression	(IN VDDI		OVE INTERVE	NTION ADI	M ONLY)		
Participant completed	ווע אטוו)	X	OAT HAITKAE	-14 HON ARI	X	Х	
Motivational Processes		^			^	^	
Participant completed		X			X	X	
Shortened Scale of		^			^		
Behavioural Change							

\* In instances where the participants surgery is cancelled and rearranged, the physical tests will need to be repeated if it is **more than 7 days** from the original surgery date. If the participant has already completed the Day of Surgery Participant Booklets they will be required to completed again.

# 9.1. Participant withdrawal and changes in levels of participation

Informed consent is defined as the process of learning the key facts about a clinical trial before deciding whether or not to participate. It is a continuous and dynamic process and participants should be asked about their ongoing willingness to continue participation at all visits. Participants should be aware from the beginning that they can freely withdraw (cease to participate) from the trial at any time. A participant may wish to cease to participate in a particular aspect of the trial.

The changes in levels of participation within the trial are categorised in the following ways:

- No trial intervention: the participant would no longer like to receive the trial
  intervention, but is willing to be followed up in accordance with the schedule of
  assessments and if applicable using any central UK NHS bodies for long-term
  outcomes (i.e., the participant has agreed that data can be collected and used in the
  trial analysis)
- No trial related follow-up: the participant no longer wishes to attend trial visits in accordance with the schedule of assessments, but is willing to be followed up at standard clinic visits (i.e., the participant has agreed that data can be collected at standard clinic visits and used in the trial analysis)
- **No further data collection:** the participant is not willing to be followed up in any way for the purposes of the trial and does not wish for further data to be collected (i.e., only data collected prior to the withdrawal can be used in the trial analysis)

The details of changes of levels in participation within trial (date, reason and category of status change) should be clearly documented in the source documents.

Participants can change their level of participation without giving a reason, although a reason would be very useful in the pilot to help assess whether it is related to the design of the trial.

BCTU should be informed of withdrawal or change in level of participation via the trial withdrawal/change of status form.

# 10. ADVERSE EVENT REPORTING

No related harms have been reported in the literature regarding App use to facilitate self-management of diet and exercise. Therefore, there is no reason to anticipate any safety concerns arising as a result of this intervention within F4S-2. Events that would be considered as adverse events (AEs) are being collected as part of the outcome measures data collection up to 30 days post-surgery this will include the following:

- Post-operative complications as per Claviden-Dindo classifications see appendix I
- In-hospital mortality
- 30 day mortality

During follow-up, the systematic collection of self-reported data as part of the clinical outcomes will be conducted, this will take place alongside routine medical note review (at mandated time points: day of discharge and 30 days follow up). This will include participant reported summaries of health care visits including any admissions to accident and emergency. The team will also capture whether there have been any deaths and cause of death. The events listed above (with reference to Appendix I) will be reviewed by the Data Monitoring Committee (DMC) at regular intervals as part of the main data set.

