#### 7.3.1 Structured Home Exercise Programme

Participants are guided through a series of screens to build their own programme, including a range of strengthening, mobility and cardiovascular exercises. Baseline suggestions on programme level/ intensity are made based on a 'sit to stand test' conducted within the App. Once the programme is built, participants are encouraged to exercise daily to achieve

.....

150 minutes of exercise/week as per pulmonary rehabilitation guidelines [38]. Heart rate is recorded using a wearable sensor provided free of charge to the participants. Once each exercise is completed, the participant inputs their perceived intensity using the BORG perceived exertion scales to the App [40]. This data is used to encourage the participant via personalised messages to increase or decrease intensity at the next session to achieve the target intensity of BORG perceived exertion as per rehabilitation guidelines [38]. Regular data uploads allow health care professionals to view participants' progress, whilst the App allows the participant to request support from the health care professional if required. Only these health care professionals can view the information within the App. They will be able to see alerts from the participant through the admin page. The App app has safety messages to advise participants to seek medical advice when required (in the same way that usual care patients are directed to contact depending on the situation)

Participants are also able to record any other exercise they undertake e.g. swimming, running etc. Whilst the programme is focussed on pre-surgery, exercise can also benefit recovery post-surgery [41], so the participant will be permitted to use the programme after surgery for a period of 6 weeks, but it will be adapted/reset according to participants' post-surgery 'sit to stand test' performance (on postoperative day 1).

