### 7.3.2 Individualised Nutritional Conditioning

At the time of enrolment, participants complete a nutritional screening questionnaire (Patient-Generated Subjective Global Assessment (PG-SGA score)) within the App [42], which tailors' nutritional advice and supplementation based on symptoms and nutritional risk. All participants in the F4S arm will be encouraged with the aid of a "ready reckoner" to intake a high protein (20g) snack within 90 minutes of exercise to stimulate muscle protein synthesis and a positive protein balance. Participants will record in the App when they have taken a protein snack. Participants deemed 'Medium risk' (PG-SGA score 4-9) will be started on a low volume, high calorie, high protein oral nutritional supplement (ONS) containing at least 18g of protein twice a day until surgery. High risk participants (score > 9) will be started on supplements as above and referred to a dietitian for optimisation of supplement prescription [42, 43].

While the recommendations above are aligned with national guidance, sites can adhere to local policies. Standard care will be followed regarding the supplementation and monitoring.

Whilst the programme is focussed on pre-surgery, it is acknowledged that after surgery, calorie and protein requirements are high at a time when intake may be impaired by the after effects of surgery. Therefore, nutritional intervention will continue for 4 weeks post-

surgery. Participants will complete the PG-SGA using the App on postoperative day 1 and based on this nutritional advice and supplementation will be tailored as described above.

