### 7.5. Continuation of intervention after the trial

The App is designed specifically to assist participants in the weeks immediately prior to, and subsequent from, their surgery. Therefore, there is no further benefit expected after the 6 week trial period is completed.

The App will remain available for use where participants have used their own devices to download and access it, and may continue to use it. This will not be within the confines of the trial. It will be explained to participants that whilst use may continue, no further benefit is expected after the 6 week trial period is complete and it will not be monitored by the clinical team.

For participants who are provided with a tablet, the tablet will be returned and wiped of all data.

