# 7.6. Intervention Access Supply and Storage

Participants will be asked to download the F4S App to their personal device. A link to register for the App will be provided to all participants randomised to the F4S arm. For those who do not have a mobile device, tablets will be provided before surgery and for approx. 6 weeks after. The tablet devices will be distributed to the recruiting sites from the Trial Office, where they should be safely secured until provided to a participant.

When provided to a participant the equipment log should be completed to record tablet use. At the end of each participant's participation in the trial the tablet will be returned to the recruiting site. The site will maintain a log of usage of the Tablet, set used throughout the study recording the lot number used against each participant (on an equipment log). The hardware does not require any special storage conditions but should be handled with due care and in accordance with any instructions. Equipment failures will be replaced provided there is no evidence of inappropriate use or deliberate negligence, under which circumstances the Sponsor reserves the right not to re-supply the participant.

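### Systematic adverse-event collection ends at day 30, but the App exercise programme is trial intervention to 6 weeks after surgery; the time limit for in-hospital mortality is also unclear

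*Protocol*

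**What the plan says.** Section 10 (Adverse Event Reporting) sets up no separate adverse-event reporting. It relies on outcome data: such events "are being collected as part of the outcome measures data collection up to 30 days post-surgery". Three items follow: Clavien-Dindo complications, in-hospital mortality and 30-day mortality. Self-report and note review take place "at mandated time points: day of discharge and 30 days follow up". The DMC reviews the listed events. A further sentence says that deaths and their causes will be captured, and gives no day limit.

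Table 2 (Schedule of Assessments) agrees: complications are assessed at discharge and at 30 days (±7 days), and at no later contact.

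The intervention runs longer:
- Section 7.3.1: "the participant will be permitted to use the programme after surgery for a period of 6 weeks".
- Section 7.5 treats this as the trial period, after which "no further benefit is expected after the 6 week trial period is complete and it will not be monitored by the clinical team". App use falls outside the trial only after that point.
- Section 7.6, for participants without their own device: "tablets will be provided before surgery and for approx. 6 weeks after".
- Section 7.3.2, by contrast, says that "nutritional intervention will continue for 4 weeks" after surgery.

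**The concern.** By the protocol's own description, App exercise on days 31 to 42 is trial intervention. It is done at home, after the last questionnaire visit held in clinic (Section 12.3). The planned enquiry about complications has ended by then. An exercise injury or an emergency attendance in those days would have no scheduled route into the safety data, would not be graded and would not be checked against the notes. Section 10 justifies light reporting by expecting no harm from the App, and Section 3.3 rates the risk as no higher than usual care. The trial should be able to support that expectation for the whole period over which it offers the programme.

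The second part concerns a named safety item. In-hospital mortality is listed beside 30-day mortality, under an introduction that stops at day 30. Taken literally, it becomes a subset of 30-day mortality and adds nothing. Taken as death before discharge, it contradicts the introduction. Two people preparing a DMC report could count a death in hospital on day 36 differently.

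**Working it through.** The protocol gives no figure of its own for this gap, so there is none to reproduce. The check is date arithmetic followed by a search for other data that might fill the gap.

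**Inputs**
- End of event collection: day 30 (Section 10).
- Window on the 30-day visit: ±7 days, so day 23 to day 37 (Table 2).
- Post-operative App exercise: 6 weeks (Sections 7.3.1, 7.5, 7.6).
- Post-operative nutritional component: 4 weeks (Section 7.3.2).
- Minimum pre-operative App use: 2 weeks (Section 7.2).
- Participants per arm: 451, with 20% attrition allowed (Section 15.1).

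**Length of the gap**
- App exercise: 6 × 7 = 42 days. Gap = 42 − 30 = 12 days, and 12/42 = 28.6%.
- Measured from the actual visit: 42 − 37 = 5 days for the latest permitted visit, and 42 − 23 = 19 days for the earliest.
- Nutritional component: 4 × 7 = 28 days, inside the 30-day limit, so there is no gap.
- As a share of all App exposure, including the minimum pre-operative period: 12/(42 + 14) = 12/56 = 21.4%. A longer pre-operative period makes this share smaller.

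**Exposure, upper bound**
- With attrition: 451 × 0.8 ≈ 361, and 361 × 12/365.25 = 11.9 person-years.
- Without attrition: 451 × 12/365.25 = 14.8 person-years.
- Both assume that every F4S participant is still exercising with the App to day 42. Section 7.3.1 only permits post-operative use, Section 7.4 expects some participants to disengage, and no post-operative usage figure is given.

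**Other data that reach days 31 to 42**
- *Deaths.* The sentence in Section 10 on capturing deaths and causes has no day limit. Table 4 (Section 12.2) requires a change-of-status form when a site learns of a death. Coverage is partial because it depends on the site becoming aware.
- *Admissions.* The resource-use questionnaire is given at 30 days and again at 6 months, and Section 16.1 includes hospital admissions in resource use. It serves the economic analysis and is ungraded. Nothing in Section 10 says that it feeds the safety review.
- *3-month contact.* Section 9 and Table 2 list quality-of-life and mental-health questionnaires, plus motivation and behaviour-change scales in the F4S arm. There is no event item.
- *App.* Section 7.3.1 lets health care professionals see uploads and alerts, but Table 3 (Section 12.1) lists only usage and engagement data as transferred to the trials unit. The usual-care arm has no counterpart.

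**Recall interval for an event on days 31 to 42** (assuming 3 months ≈ 91 days and 6 months ≈ 183 days)
- To the 3-month booklet: 91 − 42 = 49 to 91 − 31 = 60 days.
- To the 6-month questionnaire: 183 − 42 = 141 to 183 − 31 = 152 days.

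**The case against.** The strongest reply is that the 30-day window is a stated, risk-based choice. The programme is mainly pre-operative, post-operative use is optional, the risk assessment found nothing above usual care, and Section 1.2.5 reports no adverse or serious events from home App use in the pilot study. Adherence (Section 7.8) is defined by pre-operative use and the 30-day questionnaires. All of this stands, and it keeps the consequence modest. It does not explain why collection stops before the period that Section 7.5 itself calls the trial period.

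A reader might infer that the trial holds no safety data after day 30, or that mortality collection stops there. The protocol does not support either reading: deaths and causes are to be captured without a stated limit, a form is due when a death becomes known, and admissions are within the 6-month resource-use data. What is missing is systematic, graded event collection and note review.

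A reader might also infer that a death in hospital on day 36 is counted in neither mortality item, and that the DMC never sees such deaths. The text is ambiguous, not clearly truncated. Listing the item separately suggests that death before discharge was meant, and Section 18.5 provides for safety outcomes to go to the DMC. The supportable statement is that the protocol does not settle the matter.

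Finally, a 3-month postal item also relies on recall, is answered by unblinded participants and has one reminder. That is fair, but the recall interval is about 50 to 60 days against about 140 to 150, and the same question would be put to both arms.

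**Conclusion.** The point holds in a limited form. Section 10 ends systematic adverse-event collection and note review at day 30, while Sections 7.3.1, 7.5 and 7.6 run App exercise to 6 weeks. That leaves 12 of 42 post-operative App days (29%), or 5 to 19 days depending on the visit date, without systematic, graded event collection in either arm. The 12 to 15 person-years of exposure is an upper bound, because uptake after day 30 is unknown.

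The effect on the trial's conclusions is small. Both primary outcomes are at 30 days and are untouched, the nutritional component lies within the window, and deaths and admissions are partly captured. The gap limits what the trial can report about safety over its full intervention period. The time limit for in-hospital mortality needs a definition whatever view is taken of the gap.

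This rests on reading Section 7.5's 6-week trial period as the post-operative App period, as Sections 7.3.1 and 7.6 indicate, and on there being no event item in the 3-month booklet beyond those listed in Section 9, Table 2 and Table 5.

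**What to change.** Reconcile Sections 7.3.1, 7.5 and 10 without altering the intervention:

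1. In Section 10 and Table 2, extend event collection in both arms to the end of the 6-week post-operative App period. Use one dated item in the existing 3-month booklet asking about injury and unplanned hospital or emergency attendance since the 30-day visit. The date allows events up to day 42 to be picked out, and asking from the visit itself covers the 5-to-19-day variation.
2. State that these reports go to the DMC with the other Section 10 events.
3. Define in-hospital mortality as death before discharge, whenever it occurs, so that it is distinct from 30-day mortality.
4. Record vital status and date of death on the existing 6-month form that already covers recurrence or progression. This partly overlaps the change-of-status form but does not depend on a site happening to learn of a death.
5. Keep the CCI primary outcome at 30 days.

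The cost is a protocol amendment, one booklet item and two eCRF fields, with no new visit. The downside is a slightly longer booklet and some recall error.
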